10.4 Laboratory Evaluations

The actual and change from Baseline values of clinical laboratory data (hematology, chemistry, and urinalysis) will be summarized by visit presented in a table, using continuous descriptive summary statistics at Baseline and each post-Baseline visit. For Type B, laboratory tests with both local and central versions will be combined and analyzed.

Laboratory parameters that can be graded using CTCAE will be graded. The number and percentage of subjects will be summarized for the following:

- Grade 2 and Grade 3 or higher laboratory abnormalities
- Worst post-Baseline severity grade
- Shift summary of Baseline grade to worst post-Baseline severity grade
- ALT or AST >=3xULN
- ALT or AST >=3x ULN and total bilirubin > 2x ULN

Box plots of selected hematology (hemoglobin, absolute lymphocyte count, absolute neutrophil count, platelets, white blood cell count) and chemistry parameter values (sodium, potassium, eGFR, ALT, AST) will be produced by assessment visit.

Mean +/- standard error (SE) figures will be provided for serum albumin, spot UPCR, 24-hour UPCR, spot UACR, 24-hour UACR, eGFR and Spot UPCR, spot UPCR and 24-hour UPCR, and spot UACR and 24-hour UACR overtime, for Type-B subjects only.

A by-subject listing will also be created for laboratory results in conventional units.

A by-subject laboratory findings prior to induction listing will also be created for prior to induction laboratory results in conventional units.

10.5 Pregnancy

Pregnancy testing in women of childbearing potential will be obtained with a urine and serum beta human chorionic gonadotropin test (βHCG). A pregnancy test will be performed during Screening, Day 1, Day 15, Day 29, Day 43 and at Day 57 visit in Type A subjects and during Screening, Day 1, Day 15, Day 29, Day 43, Day 57, Day 71, Day 85, Day 99, Day 113, Day 127, Day 141, Day 155, Day 169, FU2, FU3, and FU4 for Type B subjects.

Pregnancy test results, including the type of pregnancy test performed at visit will be presented in a bysubject listing.

10.6 Vital Signs

Vital signs will be collected pre-dose and 30 minutes after the injection at each dosing visit. For Type B subjects, vital signs will be measured on 2 different days at least 3 days apart at Screening. Additionally for Type B subjects, blood pressure will be measured twice at least 3 days apart at Screening. Vital signs will include systolic and diastolic blood pressures (mmHg), pulse rate (beats/min), respiratory rate (breaths/min), temperature (°C or °F) and weight (kg).

Temperature collected in °F will be converted into °C using the following formula:

Temperature (°C) = [Temperature (°F) – 32] x (5/9)

The actual and change from Baseline values of vital signs will be summarized by visit presented in a table, using continuous descriptive summary statistics at Baseline and each post-Baseline visit. In addition, number and percent of subjects with out of range vital signs at any post-baseline visit will also be summarized for the following categories:

Blood Pressure:

- SBP > 150 mmHg or DBP > 100 mmHg
- SBP <90 mmHg or DBP <60 mmHg

Heart Rate:

- < 50 beats per min

- >120 beats per minute
- \geq 30 beats per minute increase from baseline
- \geq 30 beats per minute decrease from baseline

A by-subject listing will also be created.

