Equillium, Inc. Clinical Study Protocol No. EQ001-19-002 Page 12 of 110

The MTD determination will be made based only on Type A Cohorts. Dose escalation is allowed to proceed if no predefined stopping criteria are met and the DRC recommends that it is safe to proceed.

Type B

Up to approximately 20 subjects will be enrolled and dosed in the Type B Cohort. Subjects will receive a total of 13 doses of EQ001 1.6 mg/kg administered SC every 2 weeks over 24 weeks. All subjects must be on a stable dose of mycophenolate mofetil (MMF) or mycophenolic acid (MPA) for the duration of the study. Subjects that require induction treatment with pulse steroid treatment of methylprednisolone ≥500 mg or equivalent will undergo a rapid steroid taper with a 20% reduction per week. The targeted goal is to reach a prednisone dose of 10 mg or less per day by Week 10.

The study will be conducted in 3 defined periods, described below:

- 1. Screening Period
 - a. **Type A Cohorts:** The Screening Period for Cohort A subjects will be up to 4 weeks in duration, starting with the first screening procedure in the Schedule of Events (SOE; excluding the informed consent), and completed prior to Study Day 1 (Section 5.2)
 - b. **Type B Cohort:** The Screening Period for Cohort B subjects will be up to 6 weeks in duration (excluding the informed consent) and completed prior to Study Day 1 and may be completed over the course of multiple clinic visits. (Section 5.3).
- 2. Treatment Period
 - a. **Type A Cohorts**: The Treatment Period for Cohort A subjects will be 4 weeks in duration, beginning on Day 1 with the first study drug dose. During the Treatment Period, 2 doses of study drug will be

[figure not shown]
- administered subcutaneously (SC), 1 dose each on Days 1 and 15. Subjects will return to the study site for follow-up evaluations according to the SOE (Section 5.2).
- b. **Type B Cohort**: The Treatment Period for Cohort B subjects will be 24 weeks in duration, beginning on Day 1 with the first study drug dose. During the Treatment Period, 13 doses of study drug will be administered SC, 1 dose each on Days 1, 15, 29, 43, 57, 71, 85, 99, 113, 127, 141, 155, and 169. Subjects will return to the study site for follow-up evaluations according to the SOE (Section 5.3 and Section 5.4).
- 3. Follow-up Period
 - a. **Type A Cohorts**: The Follow-up Period for Cohort A subjects will end approximately 6 weeks after the last dose of study drug (Section 5.2)

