- 6. (All Regions except Asia-Pacific [APAC]) All subjects must be on MMF/MPA 2 to 3 g/day. For subjects that require induction treatment due to newly diagnosed LN or relapsing/flaring disease, subjects can have pulse systemic corticosteroids administered as part of their induction treatment.
 - (APAC) Requires induction treatment due to newly diagnosed LN or relapsing/flaring disease. Subjects need to be on MMF/MPA (2 to 3 g/day) and pulse systemic corticosteroids as part of their induction treatment. The MMF/MPA and pulse systemic corticosteroids can be started within 12 weeks prior to Day 1 or on Day 1.
- 7. Subjects that require induction treatment must receive at least 2 consecutive days of pulse systemic corticosteroids of methylprednisolone (≥500 mg) or equivalent and be able to receive it 12 weeks prior to Day 1 or start on Days 1 and 2; all induction subjects must be able to undergo a taper of systemic corticosteroids during the first 10 weeks of treatment.
- 8. Within 6 weeks of Day 1 has adequate hematologic function as defined by
 - a. ANC $> 1.5 \times 10^9/L$
 - b. ALC $\geq 1.0 \times 10^9/L$
 - c. Platelet count $> 75 \times 10^9/L$
 - d. Hemoglobin > 8.5 g/dL
- 9. Blood pressure ≤ 170/95 mm Hg without recent clinically significant changes per the investigator
- 10. The investigator considers the protocol-recommended steroid tapering schedule to be clinically appropriate for the subject based on the subject's current status and history
- 11. Has documented elevation of ANAs in the past or currently
- 12. The dose of MMF/MPA and other SLE drug treatments (other than glucocorticoids) are expected to remain stable during the study
- 13. Restricted SLE treatments (e.g., other immunosuppressive medications, antimalarials, ACE inhibitors, and angiotensin receptor blockers) are stable and/or washed out at Screening
- 14. Most recent eGFR ≥ 40 mL/min/1.73m² during Screening
- 15. No recent clinically significant changes in eGFR (increases or decreases) per the investigator
- 16. If the subject is a female of childbearing potential, she must be willing to practice complete abstinence, or she and any male partner are required to simultaneously use 2 effective contraceptive methods, from the following list of 5 methods below throughout the study and for 130 days after the last dose of study drug:
 - A barrier (condoms, diaphragm or cervical cap) with or without spermicide;
 - A second, different barrier method (condoms, diaphragm or cervical cap);

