13.1 General Considerations

Data will be summarized using descriptive statistics (n, mean, median, standard deviation, minimum, maximum) for continuous variables and frequencies and percentages for discrete variables. All data summaries will be displayed by cohort. Data may also be pooled across cohorts. Baseline values of variables are considered the last available non-missing value prior to receiving any study drug unless otherwise specified. By-subject listings of the data will also be provided. All data summaries and listings will be produced using the SAS® software, version 9.3 or higher.

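### The SAP's high-blood-pressure count (SBP above 150 mmHg at any post-baseline visit) has no baseline condition, so Type B subjects who enter stable at 151 to 170 mmHg are always counted

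*SAP*

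**What the plan says.** SAP 10.6 (Vital Signs) plans three displays.

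- A continuous summary: "The actual and change from Baseline values of vital signs will be summarized by visit presented in a table".
- A categorical table giving the "number and percent of subjects with out of range vital signs at any post-baseline visit will also be summarized for the following categories". For blood pressure the high category is "SBP > 150 mmHg or DBP > 100 mmHg" and the low category is SBP below 90 or DBP below 60. Both are absolute limits. The heart-rate part of the same list has absolute limits and also change categories, such as a "30 beats per minute increase from baseline" of at least that size, with the matching decrease.
- A by-subject listing.

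Elsewhere the SAP refers its categorical safety tables to baseline. SAP 10.4 plans a "Shift summary of Baseline grade to worst post-Baseline severity grade" for laboratory data, and SAP 10.7 has QTcF categories by increase from baseline as well as absolute ones.

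Protocol 9.1.2, criterion 9, sets the Type B entry limit: "Blood pressure ≤ 170/95 mm Hg without recent clinically significant changes per the investigator". Protocol 9.1.1 lists no blood-pressure limit for Type A. Protocol 13.1 gives the general baseline rule: "Baseline values of variables are considered the last available non-missing value prior to receiving any study drug unless otherwise specified". On size, the protocol synopsis says "Up to approximately 20 subjects will be enrolled and dosed in the Type B Cohort".

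**The concern.** The systolic limit for being counted as out of range lies inside the range that the protocol accepts as stable at entry. A subject who enters at 160/90 mmHg and never changes appears in the table in the same way as one who enters at 125/80 and rises to 160/90.

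Vital signs are part of the primary safety endpoint (Protocol 8.6.1, SAP 4.1). The study is open label and every subject receives EQ001, so no comparator shows how much of the percentage reflects blood pressure at entry. The protocol also lists hypotension and hypertension among the signs of a possible injection-related reaction (8.3.3.2), so new departures in either direction are of interest. A categorical table is normally where a reader looks for change in a few subjects that by-visit means would hide.

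**Working it through.** The documents state no expected frequency for this table, so there is no figure to reproduce.

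**Step 1. Entry limit against cut-off** (Protocol 9.1.2 criterion 9; SAP 10.6).

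- Systolic: 170 − 150 = 20 mmHg. The entry limit lies above the cut-off, so an eligible subject can have an unchanged SBP of 151 to 170 and meet the category at every visit.
- Diastolic: 95 − 100 = −5 mmHg. The entry limit lies below the cut-off, so there is no overlap.

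This step needs no assumption.

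**Step 2. Weight of one subject.** With 20 Type B subjects, 1/20 = 5 percentage points.

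**Step 3. How many subjects.** The documents give no baseline distribution of SBP, so the share f of subjects who enter stable at 151 to 170 is an assumption, shown as a range. The expected number is 20f, and the chance of at least one is 1 − (1 − f)^20.

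| Assumed f | Expected number of 20 | Percentage points added | Chance of at least one |
|---|---|---|---|
| 5% | 1 | 5 | 0.64 |
| 10% | 2 | 10 | 0.88 |
| 20% | 4 | 20 | 0.99 |
| 30% | 6 | 30 | >0.99 |

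**Step 4. Subjects near the cut-off.** Type B has 13 dosing visits, 12 of them after Day 1. Assume a constant usual SBP μ, independent normal readings, one per visit, and a within-subject SD of 8 to 12 mmHg (not in the documents). The chance of at least one reading above 150 in 12 visits is 1 − Φ((150 − μ)/SD)^12.

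| Usual SBP | SD 8 | SD 12 |
|---|---|---|
| 130 | 0.07 | 0.44 |
| 140 | 0.74 | 0.93 |
| 145 | 0.976 | 0.993 |
| 150 or more | about 1.00 | about 1.00 |

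Positive correlation between visits would lower the values below 1.

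**Step 5. What each remedy does under the same model.**

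- Requiring that the category was absent at baseline removes the subject constantly at 151 to 170 (from always counted to never counted as new).
- It does little for a subject with usual SBP 145 and a baseline reading of 150 or less. Later readings are independent of the baseline reading, so the chance of being flagged is still 0.976 to 0.993.
- A row for a rise or fall of at least 20 mmHg at any of 12 visits, against a single-reading baseline, flags an unchanged subject with probability 0.44 (SD 8) to 0.87 (SD 12). For a rise only, it is 0.22 to 0.48. These do not depend on the entry level.

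**The case against.** The strongest reply is that the same section already uses baseline. The out-of-range count is additional to a by-visit summary of change from baseline, which covers systolic and diastolic pressure, and to a listing that shows who entered high. With about 20 Type B subjects that listing can be read by eye. Adverse events give a further route: Protocol 12 counts worsening of a pre-existing condition, and SAP 10.3 requires onset or worsening after dosing, so stable hypertension should not become a treatment-emergent event. The table's label is also literally true of a subject at 160 mmHg, and the SAP uses absolute any-visit limits elsewhere (ALT or AST at least 3 times ULN, PR above 200 msec).

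Most of this stands, and it limits the point to one table. It does not remove it. By-visit means can hide a rise in a few subjects. The laboratory, QTcF and heart-rate displays pair absolute limits with baseline-referenced ones, and blood pressure has no such pair.

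A reader might go further and infer three things that the documents do not support.

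- That the plan cannot show whether EQ001 raises blood pressure. The change summary and the listing bear on that directly.
- That a comparison of Type A with Type B is distorted. No such vital-sign comparison is planned. SAP 6.1 limits pooling across A and B to adverse-event summaries, and 2 doses against 13 would make any-visit percentages differ under any cut-off.
- That a large share of the cohort, say 20% to 40%, will be falsely counted. An entry ceiling is not an expected value, and the documents give nothing from which to derive the share.

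**Conclusion.** The point holds for the categorical blood-pressure table in SAP 10.6. An eligible Type B subject unchanged at a systolic pressure of 151 to 170 mmHg is always counted, at 5 percentage points each if 20 are enrolled, and the table cannot tell this from a new rise. That follows from the two documents alone. The number of such subjects is unknown, and the 5% to 30% shares above are illustrations.

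The conflict with the entry limit concerns systolic pressure in Type B only. The missing baseline condition also applies to the diastolic and low-pressure limits and to Type A, but no listed entry limit conflicts with the cut-off there. The impact is modest, because change from baseline and individual values are reported elsewhere in the same section. The point concerns the summary table and takes no view on the entry limit itself.

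**What to change.** In SAP 10.6, add a shift table from baseline blood-pressure category (high, in range, low, by the SAP's own cut-offs) to worst post-baseline category, with the worst value taken separately on the high and the low side. At the least, add a row for subjects out of range after baseline and not at baseline. State which baseline applies. Keep the present any-visit count as an extra row.

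A change-from-baseline row for blood pressure is optional. If one is added, a footnote should say that visit-to-visit noise alone will flag many stable subjects: about 44% to 87% for a rise or fall of at least 20 mmHg over 12 visits, under the assumptions in the working.

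The cost is SAP wording and one more programmed table, with no new data and no change to eligibility or conduct. SAP 2.2 places the final analysis after the Type B database lock, so a change made before lock would still be prespecified for Type B. The shift table has two limits: it does not remove noise for subjects whose usual pressure is near 150 mmHg, and a subject high at baseline who rises further stays in the high-to-high cell, so the change summary and listing are still needed.

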10.7 ECG

A standard 12-lead ECG will be performed at Screening, Day 1, Day 29, FU2/Day 57, and Early Termination for Type A Cohort Subjects and at Screening, Day 1, Day 43, Day 85, Day 141, Day 169, FU4/Day 253, and Early Termination for Type B Subjects. The subjects will be in a seated, semi-recumbent, or supine position in a rested, calm state for at least 10 minutes before ECG assessment is performed. Any clinically significant abnormal ECG findings will be recorded as an AE.

The actual and change from Baseline values of ECG parameter HR and intervals (PR, RR, QRS, QTcF) will be summarized by visit presented in a table, using continuous descriptive summary statistics at Baseline and each post-Baseline visit. ECG overall interpretation will be summarized by visit as a categorical variable (normal, abnormal – not clinically significant, abnormal – clinically significant).

QT interval corrected for heart rate will be calculated using the Fridericia's formula: QTcF=10xQT/RR^{1/3},

where RR represents RR interval measured in milliseconds.

Worst post-baseline increase in QTcF by visit will be summarized for the following:

- <= 0 msec increase from baseline
- >0 <= 30 msec increase from baseline
- >30 <= 60 msec increase from baseline
- >60 msec increase from baseline

Outlier ECG intervals will be summarized for the following:

- PR > 200 msec
- HR > 120 or < 40 bpm
- QTcF increased by >30 msec from baseline
- QTcF increased by >60 msec from baseline
- QTcF > 480 msec
- QTcF > 500 msec

A by-subject listing will also be created.

Statistical Analysis Plan Sponsor: Equillium Inc.; Protocol No.: EQ001-19-002
